The treatment is based on polychemotherapy, which is the combination of antineoplastic drugs that seek to control cell growth and replication as well as destroy neoplastic cells in different phases of the cell cycle. In general, chemotherapy in patients with LLA consists of three phases: Induction, consolidation and maintenance, during which the prophylaxis of the central nervous system is incorporated, with intrathecal chemotherapy or high doses of chemotherapy.⁷

Induction aims to eradicate more than 99% of leukemic cells, restore normal hematopoiesis and the patient's physical condition. This phase of treatment includes the administration of glucocorticoids, with dexamethasone being the most used because it has better penetration to the central nervous system, associated with vincristine, L-asparaginase and an anthracyclinc. With induction, usually more than 90% of patients achieve complete remission. The consolidation phase improves the remission achieved by induction; Commonly the regimens include high doses of methotrexate associated with 6-mercaptopurine. The maintenance phase aims to maintain the remission already achieved. Most regimens include the combination of weekly methotrexate with daily 6-mercaptopurine. The total duration of treatment should be from 2 years to 2 years and six months.⁸

Chemotherapeutic protocols are the result of the collaboration of different study groups, in 2015 Pui et al.,⁹ conducted a review of the literature to analyze the impact of collaborative studies on advances in biology and treatment of LAL in children and adolescents, finding a 5-year overall survival rate of 82 to 93.5%. However, the substantial proportion of survivors face long-term complications; Therefore, the development of new protocols is currently aimed at optimizing the use of existing antileukemic agents, by evaluating the pharmacogenetics of normal host cells to avoid insufficient or excessive treatment.¹⁰

Oral complications secondary to chemotherapy

The lack of selectivity of antineoplastic drugs produces toxic effects in normal cells, especially in those with high replication rate, such as the cells of the basal layer of the epithelia, in which their renewal capacity is altered resulting in various complications. That is why in patients with hematologic malignancies such as LLA, oral lesions may occur secondary to direct damage of the lining epithelium by chemotherapy.⁶

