The most frequent oral complications that have been reported in pediatric patients under chemotherapy are oropharyngeal mucositis (OM), xerostomia, caries and gingivitis, followed by opportunistic infections, which occur in up to 30% of cases; being more frequent those of fungal origin, although they can also be of bacterial or viral origin (candidiasis, cold sores, aphthous stomatitis and angular cheilitis). In the Mexican population, study by Castellanos et al., On oral lesions in children with acute lymphoblastic leukemia of the National Institute of Pediatrics, found that during the first 8 weeks of onset of chemotherapy, 71% of children developed some oral lesion the most frequent being OM (65%); which in severe grades (III or IV) was associated with neutropenia and malnutrition.⁶

Oral Mucositis

Oropharyngeal mucositis (OM) is a lesion of the oral and oropharyngeal mucosa that appears as a result of inflammatory changes in epithelial and subepithelial cells caused by the cytotoxic effects of chemo or radiotherapy.¹¹

The OM consists of four phases: 1) initial inflammation, 2) vascular and epithelial rupture 3) ulcerative / bacteriological and 4) healing. (7) It begins 3 to 10 days after the start of chemotherapy and may persist for 3 weeks. It reaches its maximum peak around 7 to 14 days and subsequently resolves slowly unless it is complicated by an infection; while, better resolution has been associated with neutrophil recovery.¹²⁻¹⁴

OM occurs at any age; however, it has been observed that the prevalence is higher in pediatric patients than in adults, which can be explained by the higher rate of cellular replication during childhood. It is estimated that 52 to 80% of children undergoing chemotherapy will experience some degree of OM, which varies according to the type of cancer and antineoplastic treatment. In general, children with hematologic malignancies present more frequently with OM than those with solid tumors.¹⁴

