Exclusion criteria. Patients with another disease or systemic condition in addition to ALL. Presence of oral infections such as candidiasis, herpetic gingivostomatitis, reactive oral lesions. Children with Down syndrome, patients allergic to zinc or mannitol.

Elimination criteria: Patients who present with hypersensitivity to zinc or placebo (mannitol), those who develop a systemic condition that modifies their treatment or prevents oral care, as well as patients requesting to leave the study.

Definition of the variables

INTERVENTION VARIABLE				
	CONCEPTUAL DEFINITION	OPERATIONAL DEFINITION	TYPE	MEASUREMENT
ZINC	Trace element found in most of the body's cells, having catalytic, structural and cellular regulation functions.	Food supplement based on zinc sulfate in doses of 50-100 mg / day for prevention and treatment of oropharyngeal mucositis .	Qualitative Nominal	1. Apply 2. No apply

DEPENDENT VARIABLES				
ORAL HYGIENE	Combination of physical and chemical measures to control the formation of bacterial plaque, which is the most important risk factor in the development and evolution of caries and periodontal disease.	Oral hygiene registered with the O'Leary index (bacterial plaque on dental surfaces identified by a developer. It is obtained from the sum of stained dental surfaces / total surfaces, multiplied by 100.	Qualitative Ordinal	1. Good 0% to 15%: 2. Regulate 16% to 49%: 3. Poor: 3.50% to 100%:
OM RECOVERY DAYS	Days in which some degree of OM is clinically observed until healing.	Number of days from the clinical diagnosis of OM (Grade ≥ 1) to recovery of the oral epithelium.	Continuous	1,2 ,3 4, 5...

INDEPENDENT VARIABLES

ORAL MUCOSITIS	Inflammatory reaction that affects the entire gastrointestinal tract from the mouth to the anus caused by chemo and / or radiotherapy.	Inflammatory reaction of the oropharyngeal mucosa to chemotherapeutic drugs, according to the WHO scale.	Qualitative Ordinal	Grade 0. Healthy Grade 1. Erythema Grade 2. Ulcers Grade 3. Extensive ulcers Grade 4. Ulcers and necrosis.
PAIN	Localized and subjective sensory perception that is the result of an excitation or stimulation of specialized sensory nerve endings.	Visual scale of facial expressions	Qualitative Ordinal	0-2 No pain 3-4 Mild 5-6 Moderate 7-8 Intense 9-10 Maximum

SOCIODEMOGRAPHICAL VARIABLES

	CONCEPTUAL DEFINITION	OPERATIONAL DEFINITION	TYPE	MEASUREMENT

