AGE	Life time elapsed from birth to the current date.	Life time in years recorded in the clinical record.	Quantitative Discreet	Years 0 a 18
SEX	Physiological and sexual characteristics with which men and women are born.	Biological characteristics recorded in the clinical file as female and male.	Qualitative Nominal Dichotomous	1. Female 2. Male

CONFUSORY VARIABLES				
ACUTE LEUKEMIA LYMPHOBLASTICS (LAL)	Neoplastic disease that results from a clonal proliferation of lymphoid precursors (lymphoblasts), which infiltrates bone marrow, produces a variable degree of pancytopenia and can compromise different organs and / or systems.	Type of leukemia recorded in the clinical file according to the immunophenotype.	Qualitative Nominal	1. Pro B leukemia 2. Common leukemia 3. Pre-B leukemia 4. Mature leukemia B 5. T leukemia (precursors) 6. T leukemia (mature)
NEUTROPENIA	Reduction of peripheral blood neutrophil count .	Absolute neutrophil count obtained by laboratory test (blood count).	Qualitative Ordinal	0. Absence of neutropenia 1. Mild: 1,000-1,500 / ml 2. Moderate: 500-1,000 / ml 3. Severe: <500 / ml
OPPORTUNIST INFECTIONS	Infections in immunosuppressed patients, whether of bacterial, fungal or viral origin.	Record of suggestive lesions by C. albicans and determination by means of KOH, suggestive lesions of herpes and determination by PCR, suggestive bacterial lesions and detection through cultures.	Qualitative Nominal	0. Absent 1. Fungal 2. Bacterial 3. Viral

STUDY DESIGN

Double blind clinical trial

Sampling: Sequential non-probabilistic until the required number of participants is completed.

Randomization: sealed envelopes for group assignment.

Sample size calculation

Formula for the difference of proportions (incidence of OM).

$$\frac{[Z_{\alpha} \sqrt{2\pi_1(1-\pi_1)} - Z_{\beta} \sqrt{2\pi_1(1-\pi_1) + 2\pi_2(1-\pi_2)}]^2}{(\pi_1 - \pi_2)^2}$$

Assumptions:

$$\alpha = 0.05$$

$$\text{Power} = 0.90$$

Rambod study findings: The effect of zinc sulfate on prevention, incidence, and severity of OM in leukemia patients undergoing chemotherapy.

$$Z_{\alpha} = 1.96$$

$$Z_{\beta} = -0.84$$

$$n = 86$$

$$\pi_1 = 75\%$$

$$\pi_2 = 47\%$$

$$\pi_1 - \pi_2 = 28\%$$

$$\frac{[1.96 \sqrt{2(0.75)(0.25)} - (-0.84) \sqrt{(0.75)(0.25) + 2(0.47)(0.53)}]^2}{(0.75 - 0.47)^2} = 46$$

41/5000

15% losses = 53 patients per group

Statistical Analysis Plan

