Descriptive statistics will be used to characterize the population using measures of central tendency and dispersion for continuous variables and distributions of relative and absolute frequencies for categorical variables. Independent t-test and Chi-square test for the difference between the two study groups. Analysis of variance (ANOVA) to compare the two groups with respect to the OM in the five time periods.

METHODOLOGY

Randomization

The randomization will be taught by [name] [name], assigned to the Oncology service, who is unaware of the objective of the study.

The randomization technique will be carried out through sealed envelopes, which will indicate the bottle that will correspond to the patient, identified as treatment "A" and "B". Likewise, to ensure that the groups are balanced, blocks of 6 sealed envelopes containing 3 patients will be made for each group.

Blinding

The patient and the investigator will be blinded; for this, the 50 mg zinc and placebo tablets will be similar in size, color, shape, weight and taste; the bottles will be classified into codes A and B, which in turn will have the same shape, size and color. All of the above will be done through the Pharmaceuticals GREMAR S.A. de C.V., which is a Mexican company that has a line of food supplements located in Mexico City.

An independent investigator (who will be blinded for the purpose of the study) will be requested to receive the medications (zinc / placebo) prepared by the Pharmaceuticals GREMAR S.A. of C.V., so that it provides to the principal investigator only the bottles coded as "A" and "B". At the end of the intervention, the independent investigator will be asked to reveal the coding of the medications to determine which group (Group 1 placebo or Group 2 zinc) corresponds to treatment A and B respectively.

Instruments

WHO OM scale

The oral mucositis scale proposed by the World Health Organization (WHO) in 1979 will be used. This instrument was designed based on objective signs (erythema or ulcer) and subjective signs (mucosal sensitivity, ability to swallow).

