Group 2 (oral care + zinc): gentle tooth brushing with soft-bristle brush 3 times a day and mouthwash with baking soda after each meal (1/4 of tablespoon of baking soda dissolved in water to make a mouthwash for 3 minutes) plus the consumption of 1 or 2 oral zinc tablets (50-100 mg / day of zinc sulfate), from day 1 of chemotherapy. (See Flowchart 1).

Zinc dose determination

The studies described in Table 2, have used zinc doses of 50 to 150 mg divided into 2 to 4 daily doses in adult patients, which was determined from the study conducted by Ertekin et al. Because our study would be the first to evaluate the effectiveness of zinc for the prevention of OM in children, there is no reference dose in previous studies.

Due to the above, an exhaustive review of the literature on zinc requirements, therapeutic doses and toxic doses was made (Table 1), which are summarized below:

- ✓ Diarios Daily zinc requirements in children: 5 - 10 mg / day in children under 4 years, 10 mg / day in children 5 to 10 years and 15 mg / day from 11 years.
- ✓ Dose used to treat diarrhea: 10 to 40 mg / day in children older than 6 months.
- ✓ Treatment for Wilson's disease or zinc deficiency: 50 mg / day in children under 6 years, 75 mg / day from 6 to 16 years and in adults up to 150 mg / day.
- ✓ Toxic dose: 1 to 2 g / day

Considering the above information, as well as the reported doses of the use of zinc for the treatment of OM, it was decided to establish for this study the doses of zinc by age as follows:

- Patients under 10 will receive 50 mg / day (1 tablet daily).
- Patients aged 11 to 18 will receive 100 mg / day (2 tablets daily).

The characteristics of the tablets are described in Annex VIII. Zinc / Placebo features.

OM treatment

In the case that the patients attend with some degree of OM, the intervention will continue as follows:

For the follow-up of the OM, observations will be made from the beginning of the table until the remission (2 to 3 weeks).

The treatment of the OM will be the same, regardless of the group to which they are assigned, and will consist of:

Mouthwashes with Gelcliar® ® administered 30 minutes prior to food intake until box remission. In addition, oral care measures and zinc / placebo administration will continue.

Pilot test

The pilot test will be carried out once the protocol is approved by the ethics and research committee of the National Institute of Pediatrics.

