Six randomized patients with a recent diagnosis of childhood cancer who start chemotherapy will be selected, data from the clinical record will be obtained to determine if it meets the inclusion criteria. The patient identified as eligible will be visited at his place of hospitalization or in the outpatient office of the Oncology Service.

The intervention will be assigned under the balanced block scheme. Children will be randomly assigned to each of the two treatment groups using sealed envelopes.

The sequence of procedures and the complete description of the instruments can be found in the Annex "Pilot test applicator manual".

[figure not shown]
Information collection method

A data record sheet will be filled out that includes the patient's identification form (name, age, sex), type of ALL, chemotherapy phase and blood count; which will be obtained from the clinical file. It will also include the table for the determination of the WHO OM scale, the oral hygiene index and the opportunistic infection registry.

Registration and processing method.

[figure not shown]
The data will be recorded in an Epidata database and analyzed using the STATA 14 statistical program.

FLOWCHART 1

In the previous study by Rambod et al. (12), a difference in the incidence of OM of 28% was obtained and from this, for the present study the estimated sample size was 106 subjects.

Complying with one of the principles that govern clinical trials, which is to reduce the risk of the operated subjects to the minimum possible, in case of observing adverse reactions the suspension of the study will be indicated; while if there are no complications, recruitment will continue until a sample size of 53 subjects is met and at this point the intermediate analysis will be performed as shown in Flowchart 2.

ETHICAL CONSIDERATIONS

In accordance with the principles and guidelines established by good clinical practices (BPC), in accordance with the principles set forth in the Helsinki Declaration of 1964 and with the support provided in the General Health Law, in the Regulations of the General Health Law in the area of provision of Health Care Services, which establishes that the individual welfare of the subjects must sometimes prevail in a study, over the interests of science and the community.

This study will be carried out with the strict observation of the recognized scientific principles and respect, handling the affected data anonymously and confidentially.

Consent

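### The cycle-1 day-1 mucositis grade is a baseline but is analysed as an outcome, and OM present at entry could be counted as incident OM

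*Combined protocol and SAP*

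**What the plan says.** The Summary and the section on stages of the study and data collection set OM reviews on days 1, 4, 7, 14 and 21 of each chemotherapy cycle. The Statistical Analysis Plan then calls for "Analysis of variance (ANOVA) to compare the two groups with respect to the OM in the five time periods". Five review days and five periods correspond, and no text sets day 1 apart as a baseline or adjusts for it.

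Study tablets start on day 1 of chemotherapy. On the timing of OM, the Background section on oral mucositis states: "It begins 3 to 10 days after the start of chemotherapy and may persist for 3 weeks".

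The oral exclusion under Selection criteria reads: "Presence of oral infections such as candidiasis, herpetic gingivostomatitis, reactive oral lesions". OM is not named. Children with relapsed ALL are eligible alongside the newly diagnosed. An oral examination is planned on day 0, but it is described for the hygiene index and brushing instruction; no WHO grade at that examination is mentioned.

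The variable definitions describe OM as a reaction of the mucosa to chemotherapy drugs, graded on the WHO scale. Recovery days are counted from clinical diagnosis at grade 1 or more. Neither the variable definitions nor the Statistical Analysis Plan defines a new case of OM or the set of children at risk of one.

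**The concern.** Specific objective 1 and the hypothesis concern the incidence of OM, and the sample size rests on an incidence comparison. A prevention endpoint needs a starting state: a child already at grade 1 or more before the first tablet cannot have that lesion prevented. If such children count as cases, they raise the incidence in both arms and narrow the difference. If their recovery clock starts at the first reading, recovery time includes lesions that predate the trial.

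A related problem affects the ANOVA. On the protocol's own account of onset, the first reading of cycle 1 cannot show an effect of zinc. Averaging it with the later readings shrinks the estimated group difference.

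**Working it through.** **1. The plan's own figure.** Inputs from the sample size section: 75% and 47% incidence, z = 1.96 and 0.84 (in size), 15% losses. The expression as substituted there is

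[1.96·√(2·0.75·0.25) + 0.84·√(0.75·0.25 + 2·0.47·0.53)]² / 0.28² = (1.200 + 0.696)² / 0.0784 = 45.84, rounded to 46.

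Then 46 × 1.15 = 52.9, which gives "15% losses = 53 patients per group". With 15% lost, 53 × 0.85 = 45.05, so about 45 per arm are evaluable. A z of 0.84 corresponds to 80% power although the section states 0.90. That is a separate matter, but it means there is little slack.

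**2. Incidence if OM at entry is counted.** Let f be the share of each arm with OM at entry. The documents give no value, so 3%, 5% and 10% are assumptions. Each incidence p becomes f + (1 − f)p, and the difference becomes (1 − f) × 28 points.

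Power (two-sided 0.05, normal approximation, d the difference, p̄ the mean of the two incidences) is

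Φ{ [d√n − 1.96·√(2p̄(1 − p̄))] / √(p₁(1 − p₁) + p₂(1 − p₂)) }.

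With f = 0 and n = 45: (0.28 × 6.708 − 1.96 × 0.690) / 0.661 = 0.797, so power is 78.7%.

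| f (assumed) | Control | Zinc | Difference | Power, entry OM counted, n = 45 | Power, entry OM left out, n = 45(1 − f) |
|---|---|---|---|---|---|
| 0% | 75.00% | 47.00% | 28.0 | 78.7% | 78.7% |
| 3% | 75.75% | 48.59% | 27.2 | 76.6% | 77.4% |
| 5% | 76.25% | 49.65% | 26.6 | 75.1% | 76.6% |
| 10% | 77.50% | 52.30% | 25.2 | 71.4% | 74.2% |

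The last column keeps 75% against 47% and reduces only n. Leaving such children out without replacing them regains about 1 to 3 points of power.

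**3. The five-time mean in cycle 1.** If the group difference is D on days 4, 7, 14 and 21 and zero on day 1, the mean over five times is 4D/5, one fifth smaller. Whether power is lost depends on the day-1 variance.

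- *Day-1 grades vary like later ones.* Assume a common variance and a common correlation ρ between readings. The variance of the mean is proportional to (1 + 3ρ)/4 over four times and (1 + 4ρ)/5 over five. The ratio of signal to standard error is multiplied by 0.8·√{[(1 + 3ρ)/4] / [(1 + 4ρ)/5]}. For ρ = 0.2 this is 0.8·√(0.40/0.36) = 0.843; for ρ = 0.8 it is 0.8·√(0.85/0.84) = 0.805. A four-time analysis with 80% power has a ratio of 2.80, so power falls to Φ(2.80 × 0.843 − 1.96) = 66% or Φ(2.80 × 0.805 − 1.96) = 62%. The range of ρ is assumed.
- *Every child is grade 0 on day 1.* The mean and its standard error both shrink by 0.8, the ratio is unchanged, and power stays at 80%.

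**4. Later cycles.** Reviews recur in each cycle. If there were three cycles (assumed), the cycle-1 day-1 reading would be 1 of 15, and a mean over all readings would shrink by 1/15, about 7%.

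**The case against.** Much of the case on the other side stands.

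- *The plan does not say that OM at entry counts as a prevention failure.* A reader might infer that it does, but the documents are silent. The definition of OM as a reaction to chemotherapy drugs arguably leaves out lesions that predate chemotherapy in a newly diagnosed child. It does not settle the matter for relapsed children, whose lesions may come from earlier chemotherapy.
- *The OM treatment section.* The sentence "In the case that the patients attend with some degree of OM, the intervention will continue as follows" might be read as covering children who enter with OM. The word for continuing presupposes that tablets have begun, so it concerns OM arising on treatment and cannot support this point.
- *Methotrexate.* It is tempting to apply the Background's 40-60% OM figure to children relapsing on weekly maintenance methotrexate. That figure covers classes of drugs, and the same paragraph says risk depends on dose, duration and route. It gives no entry prevalence.
- *Reactive oral lesions may be meant to include OM.* Possibly, but the phrase sits in a list of oral infections, and assessors at two hospitals could apply it differently.
- *Randomisation balances lesions at entry.* It does so in expectation, so neither arm is favoured.
- *The ANOVA may not average over time.* The plan does not say that it does. A group-by-time interaction test is not diluted in this way, and a day-1 reading is useful to it. If all children start at grade 0, which the stated onset makes the expected case, the averaged test loses no power either.

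What remains is that a prevention endpoint has no starting state and that a reading before any possible effect is listed among the outcome times.

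**Conclusion.** The point holds as a correctable gap in the endpoint and the analysis. Cycle-1 day 1 is a baseline by the protocol's own timing; day 1 of later cycles is not. Because incident OM is undefined and OM at entry is not a named exclusion, entry lesions could be counted as new cases and could start the recovery-day count.

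The consequence is attenuation toward no difference. For incidence, an assumed 3% to 10% with OM at entry takes the 28-point difference to between 27.2 and 25.2 points, and power at 45 per arm from about 79% to between 77% and 71%. For a severity mean over the five cycle-1 readings, the difference shrinks by one fifth, but power is lost only if day-1 grades vary.

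The documents do not support the stronger readings: that entry lesions are counted as failures, that day 1 is unsuitable in every cycle, or that one arm is favoured.

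**What to change.** - Record the WHO grade at the day-0 or day-1 examination, before the first tablet.
- In the Statistical Analysis Plan, use the cycle-1 day-1 grade (or that pre-tablet grade) as a baseline covariate. Compare the groups over cycle-1 days 4, 7, 14 and 21 and over all readings of later cycles.
- Define incident OM as the first grade of 1 or more after a grade 0 reading, and count recovery days only for new OM.
- State how children with grade 1 or more at entry are handled: either name this as an exclusion or leave them out of the at-risk set for incidence.

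The cost is a few sentences; both examinations are already planned. The drawback is that a few children are not enrolled or do not contribute to incidence. If they are left out without replacement, the net gain in power is only about 1 to 3 points; excluding them before randomisation and recruiting others in their place restores the planned figure. The clearer gain is that incidence and recovery time then describe lesions that zinc could have prevented or shortened.

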oropharyngeal mucositis, how it relates to chemotherapy and the preventive measures they can perform. Finally, the complications that may occur during the OM will be explained, such as: difficulty in eating, speaking or swallowing, as well as the measures that must be taken to allow adequate recovery.

Parents will be invited to participate in the protocol explaining the objectives of the study, as well as its risks and benefits. In case of accepting to participate, informed consent and assent (in children over 12 years old) will be presented in accordance with the characteristics that are written in it.

The intervention will be assigned under the balanced block scheme. Children will be randomly assigned to each of the two treatment groups using sealed envelopes.

Oral examination, staining of dentobacterial plaque will be performed (the characteristics of the plaque revealing solution are described in the researcher's manual) for the determination of the oral hygiene index and explanation of brushing technique on day 0 of chemotherapy.

Patients who require dental caries treatment will be rehabilitated by the stomatology service according to their stomatological diagnosis and their general condition. A closed bottle containing 100 tablets (treatment A or B) will be provided according to the random assignment. It will be indicated to administer 1 or 2 tablets daily (according to the age of the patient) from day 1 of chemotherapy.

A written reminder will be provided to parents in which they must check each day if the tablet was taken.

Calls will be made every 3 days to verify that oral hygiene and tablet administration are being carried out; In addition, the reminder will be reviewed twice a week and the remaining tablets will be counted in the bottles.

During the course of chemotherapy (induction and consolidation phase) reviews will be performed on days 1, 4, 7, 14 and 21 of each cycle.

Maneuver

Group 1 (oral care + placebo): gentle tooth brushing with a soft bristle brush 3 times a day and mouthwash with baking soda after each meal (1/4 tablespoon of baking soda dissolved in water to make a mouthwash for 3 minutes) plus the consumption of 1 or 2 oral placebo tablets (mannitol) from day 1 of chemotherapy.

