To parents or to those who exercise parental rights of patients, we provide the information related to the study, both verbally and in writing. The master's student made an initial invitation to the parents or guardians of the minor for their child to participate in the study and read the "Informed Consent Letter" to state the purpose of the investigation and make a description of the same. In the case of patients older than 12 years, also read the "Informed Assent Letter". The signature of the parents and the minor is requested freely and voluntarily with the "Declaration of Consent / Informed Consent" after the purpose of the investigation has been understood and doubts have been clarified.

Confidentiality

To verify the confidentiality and privacy of the participants, the data will be stored in databases to which only the researchers of the study have access.

Risk

The study is classified with greater than minimum risk. The administration of zinc in doses of 50-100 mg / day is considered safe, since no adverse effects have been described at that dose.

Benefits

Patients participating in the study will have greater clinical control for the prevention of oropharyngeal mucositis, since they will be collected before the start of chemotherapy and notifications will be received to receive care from the Stomatology service in the case of treatment.

Although no difference is found in favor of the intervention and the necessary sea, the suspension of the study, measures will be taken to ensure that participants of both groups receive benefits by receiving educational oral care talks, identification of signs of OM, as well as Oral hygiene attachments and medications for the treatment of OM.

BIOSECURITY CONSIDERATIONS

In accordance with current regulations, the following is held:

- NOM-052-SEMARNAT-2005

It establishes the characteristics of hazardous waste, also mentions that expired and leftover drugs are considered hazardous waste and therefore, must finally be disposed of responsibly.⁴¹

- General law for the prevention and integral management of waste.

Article 31. The following hazardous wastes and products used, expired, withdrawn from trade or disposed of and which are classified as such in the corresponding official Mexican standard shall be subject to a management plan:

VIII. In accordance with the above, the remaining or expired doses of the drug (zinc sulfate) should be handled as hazardous waste and its disposal will be as follows:

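### One fixed block of 6 and two trial-wide bottle letters make up to about a quarter of upcoming letters (not treatments) predictable; individual bottle numbers would prevent this

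*Combined protocol and SAP*

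**What the plan says.** Under Methodology, Randomization, sealed envelopes tell the team whether a child gets bottle A or bottle B. For balance, "blocks of 6 sealed envelopes containing 3 patients will be made for each group", meaning six envelopes per block, three for each arm. The section on stages of the study repeats the scheme: "The intervention will be assigned under the balanced block scheme".

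Under Blinding, "the bottles will be classified into codes A and B". Tablets and bottles otherwise look alike. An independent investigator receives the product from the manufacturer, "so that it provides to the principal investigator only the bottles coded as" A and B, and discloses what the letters mean at the end of the intervention.

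Invitation comes before assignment: "Parents will be invited to participate in the protocol explaining the objectives of the study", consent and assent follow, and then the child is allocated. At that point, "A closed bottle containing 100 tablets (treatment A or B) will be provided according to the random assignment". During follow-up, "the remaining tablets will be counted in the bottles".

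On roles, the Consent section says: "The master's student made an initial invitation to the parents or guardians of the minor". Under Standardization, the same student is one of two people trained to grade mucositis on the WHO scale. The person in charge of randomization belongs to the Oncology service and does not know the study's aim.

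The text does not say that the block size is varied or withheld, that envelopes are opaque or sequentially numbered, that bottles carry individual numbers, or whether the two hospitals share one series.

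**The concern.** Sealing an envelope hides its content, but it does not hide what can be worked out from letters already given out. With a known block of three As and three Bs, the remaining letters become certain once one letter is used up. Before that point, the less-used letter is the better guess.

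Predictability before invitation matters because it could influence which families are approached. Newly diagnosed and relapsed children are enrolled together without stratification, and the Statistical Analysis Plan lists t-tests, chi-square tests and ANOVA with no covariate adjustment. Balance on risk of mucositis therefore rests on allocation being unpredictable.

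The two-code system adds a second exposure. If the meaning of a letter is revealed or guessed for one child, it is revealed or guessed for all children, past and future. The student who invites families is also trained to grade the outcome, so such a belief could affect both enrolment and grading.

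**Working it through.** **Inputs.** Block of 6, three per arm (Randomization). Two codes (Blinding). 106 allocations in total (Sample size calculation; text at Flowchart 1). Intermediate analysis at 53 subjects (same text).

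**The plan's own figure.** The plan gives no predictability figure; its sample size is used here only as the number of allocations. The printed numerical expression, [1.96·√(2·0.75·0.25) + 0.84·√(0.75·0.25 + 2·0.47·0.53)]² / 0.28², gives 45.8, rounded up to 46. Then 46 × 1.15 = 52.9, or 53 per group, and 2 × 53 = 106. The stated 106 is reproduced.

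**Certain letters per block.** There are C(6,3) = 20 equally likely orders. A letter is certain when three of the other letter have already been used.

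- 4th position: the first three letters are the same in 2 of 20 orders = 0.10.
- 5th position: one letter is used up within the first four in 8 of 20 orders = 0.40.
- 6th position: always, 1.00.
- 1st to 3rd positions: never, 0.

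The sum is 0.10 + 0.40 + 1.00 = 1.5 of 6 = 25%. As a check, the last three letters are known in 10% of blocks, exactly the last two in 30%, and only the last in 60%: 0.10·3 + 0.30·2 + 0.60·1 = 1.5.

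**Best guess (the letter less used so far).**

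| Position | 1 | 2 | 3 | 4 | 5 | 6 | Sum |
|---|---|---|---|---|---|---|---|
| P(certain) | 0 | 0 | 0 | 0.10 | 0.40 | 1.00 | 1.5 |
| P(guess right) | 0.50 | 0.60 | 0.60 | 0.70 | 0.70 | 1.00 | 4.1 |

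4.1/6 = 68.3%, against 50% for an unpredictable sequence.

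**Over the trial.**

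- 106 = 17 full blocks + 4, so 17·1.5 + 0.10 = 25.6 certain letters (24.2%). The guess is right 17·4.1 + 2.4 = 72.1 times (68.0%).
- First 53 = 8 full blocks + 5, so 8·1.5 + 0.50 = 12.5 (23.6%).
- Separate series per hospital, with assumed splits because none is given: 53/53 gives 25.0 (23.6%); 70/36 and 90/16 each give 25.6 (24.2%).

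**What different remedies achieve.** With blocks of 4, 6 and 8 in random order and an observer who knows the possible sizes and all past letters, simulation of 106 allocations gives about 2% certain letters, but a best-guess rate still near 68%. With individual bottle numbers that carry no arm information and a list kept from recruiters, there is no tally to keep: 0% certain and 50% guessed.

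**The case against.** The strongest reply is that a letter is not a treatment. Tablets and bottles are matched and an independent investigator holds the key, so knowing that B comes next favours neither arm unless the recruiter also believes something about B. This stands. A reader might infer that allocation concealment fails for a quarter of the sample. The documents do not support that: 25% is an upper bound on letters known in advance, not a share of biased enrolments.

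A reader might also suppose that side effects would give the letter away, since the Background reports nausea in 20%. That figure appears under gastrointestinal toxicity described as dose-related and is not tied to the trial's doses. The same Background calls adverse reactions rare, and the Risk section says none have been described at 50-100 mg/day. The figure cannot be used as an expected signal here.

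The deduction also has conditions. The observer must see every earlier letter and know where blocks start, across both hospitals if they share a series. The text uses the passive voice for dispensing and tablet counts, so only the invitation is clearly the student's task.

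Finally, there is limited room to steer enrolment. Sampling is sequential, new cases are sought daily, and tablets start on day 1 of chemotherapy. Waiting for a preferred letter would be hard. Selective invitation is not ruled out, however: the exclusion for any other disease or systemic condition is broad, and no log of screened or refusing families is described.

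The sealed envelopes and the uninvolved randomizer do not answer the point, because the deduction uses letters already dispensed.

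**Conclusion.** The point holds as a conditional weakness. A fixed block of 6 with two persistent letters makes on average up to 1.5 of 6 letters certain before assignment (25.6 of 106, 24%) and raises the best-guess rate to 68%. It would be wrong to infer that the last three letters of a block are often known; that happens in 10% of blocks.

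These figures assume that someone tallies all earlier letters in the series and knows the block size and starting points. The block size is printed in the protocol; access to the other hospital's letters is not settled. Selection bias needs, in addition, a belief about which letter is zinc. Nothing in the documents shows that such a belief exists or that anyone would act on it. The two-code design means that, if it did arise, it would apply to the whole trial. This is a cheap improvement that should be made, not evidence that the trial is biased.

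**What to change.** First, have each sequentially numbered envelope give an individual bottle number instead of A or B. Numbers should carry no arm pattern, and the number-to-arm list should be held only by the independent person. This removes the tally and stops one unblinding from exposing a whole arm.

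In addition, use randomly varying block sizes (for example 4, 6 and 8) that are not disclosed to recruiters, with a separate series for each hospital. Varying the block size alone is not enough, because it leaves the guess rate near 68% while letters stay visible.

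The cost is a new list and new labels, with no extra patients or staff. There are two drawbacks. An incomplete last block can leave an imbalance of at most half its size (4 children for a block of 8) in each hospital's series. Children on two tablets daily will also need arm-matched numbered resupply: at 30 days a month, 2 to 2.5 months is 2 × 60 = 120 to 2 × 75 = 150 tablets, against 100 in a bottle. The independent person would have to arrange this from the list.
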